 - Guidance to manage IV lines, pulse ox and other monitors per nursing unit leadership engagement
- Proning notation could be added to the room white board
- Materials will be provided to promote appropriate positioning (signage for patient beds)

Comparator Arm B: Usual care, patients will remain in their natural choice of position, which is anticipated to favor a supine, semi-recumbent position. Providers will be freely able to alter the protocol at their discretion in light of any patient decompensation.

Fidelity Monitoring randomly assigned within comparator arm A and arm B: A small subset of participants will be monitored using a routine, FDA-approved, wireless, single-use, disposable device adhered to the patient's chest. Upon activation, the sensor immediately begins monitoring the patient's orientation, position, movement and activity. Monitoring capability continues for 21 days. An initial run-in period will inform appropriate sensor assignments for the remainder of the study duration.

6. Reporting of Adverse Events or Unanticipated Problems

Participating in the study does not add risk related to treatment. Any risks to patients from participating in the study are limited to the collection of PHI and treatment assignment.

As such, study procedures do not represent a direct risk to participants above what they would incur during usual care. However, we recognize there may be adverse events related to the study. These include unusual clinical occurrences and the loss of privacy. These will be reported according to appropriate timelines. Complications related to clinical care are being captured routinely as outcomes and will be reported to the IRB as appropriate.

The Principal Investigator will be responsible for overseeing the safety of this trial on a daily basis and will be available at any time for questions from providers. The PI will also record adverse events and serious adverse events. Serious adverse events associated with study

Study Protocol: Version 7.0 - October 29, 2020

Full Study Title: Pragmatic Trial Exploring Impact of Patient Positioning in the Management of Patients Infected with COVID19: Supine vs. Prone

Primary Investigator: [name], MSc

procedures will be recorded in the study record and reported to the IRB within 10 business days of knowledge. Summary reports will be submitted to the IRB annually and will contain a) the number of adverse events and b) the number of protocol violations and how each was handled.

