- Maximum modified WHO ordinal scale score observed during 28 days of hospitalization, the modification is as follows:
 1. Death
 2. Hospitalized on invasive mechanical ventilation or ECMO
 3. Hospitalized on non-invasive ventilation or high flow nasal cannula
 4. Hospitalized on supplemental oxygenation
 5. Hospitalized not on supplemental oxygen
 6. Discharged/not-hospitalized (regardless of symptoms or organ support needs)
- Modified WHO COVID-19 ordinal scale measured at day 14

Safety endpoints:

- Incidence of Complications related to Positioning (e.g. accidental line displacement, vomiting, falls)

Datasets

Main Analysis

The main analysis for this study will be conducted using an intention-to-treat, or as assigned. All participants who met inclusion criteria and were randomized will be included. Participants will be grouped according to the arm to which they were allocated.

Safety Analysis

A safety analysis will be conducted to explore events associated with proning. This analysis will included all participants and events related to proning will be described regardless of study arm.

Other analyses

Neither a per protocol or complete case analysis is expected. A per protocol analyses might be justified if the number of major protocol deviations (including cross overs) exceeds about five in both arms combined.

Sensitivity analysis

This study was originally designed as a single-center pragmatic randomized controlled effectiveness trial. As the Covid-19 case waxed and waned across the country, and as demand for evidence for proning increased, the decision was made to open additional sites. One additional site was opened, which contributed less than 10% of participants to the dataset. We will repeat our main analyses excluded this additional site. If there are considerable differences, then we will report single site data.

Statistical Approach

Descriptive Analysis

Initially, we will describe the study cohort, both overall and grouped by intervention assignment. To characterize the study sample, demographic, clinical, and lab data will be described overall

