and by group. Groups will not be formally compared used statistical tests; differences and confidence intervals of differences may be reported. All categorical variables will be described using frequencies and proportions, and continuous variables will be described using mean, standard deviation, and percentiles (i.e. 25th , 50th , 75th). Missingness will be recorded for each variable. To further assess the distribution of variables, graphical summaries will be displayed using box-plots, dot-plots, violin-plots, and/or histograms. At a minimum, the following baseline variables will be described:

- Age (years)
- Sex (Male, Female, Not reported)
- BMI – kg/m²
 - Obesity (None, Stage I BMI 30.0 -34.9; Stage II BMI 35.0 – 39.9; Stage III BMI>=40.0, Not reported)
- Race (American Indian/Alaska Native, Asian, Black/African American, White, Other, Not reported)
- Ethnicity (Hispanic or Latino, Not Hispanic or Latino, Not reported)
 - Ethnicity may be combined with race
- Elixhauser Score
- Number of coexisting conditions (None; One; Two or more)
- Coexisting conditions (Yes/No)
 - Any
 - Diabetes
 - Hypertension
 - Underlying Respiratory Disease
 - Heart Disease
 - Renal Disease
 - Malignancies
- Smoking Status (as documented in the EMR)
- Renal replacement therapy required at enrollment (Yes/No)
- Vasopressors required at enrollment (Yes/No)
- Score on ordinal scale at enrollment (Hospitalized on low flow supplemental oxygen; Hospitalized on high flow supplemental oxygen; Hospitalized on non-invasive ventilation)

Subsequent to characterizing the cohort at baseline, we will explore and describe the outcome variables overall and grouped by study arm. We will take the same approach as for the cohort descriptors, using comprehensive summary statistics and graphical representations as appropriate. For depicting clinical course, alluvial or Sankey plots maybe be used.

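### The SAP counts only safety events related to proning, which is likely to under-count events in usual care, and its safety text commits to no comparison by assigned arm

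*SAP*

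**What the plan says.** The SAP (Safety endpoints) lists one safety endpoint: "Incidence of Complications related to Positioning (e.g. accidental line displacement, vomiting, falls". The reference is to positioning in general, so a complication in a supine patient could qualify.

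The Safety Analysis paragraph, under Datasets, is narrower. It opens "A safety analysis will be conducted to explore events associated with proning", takes in all participants, and adds that "events related to proning will be described regardless of study arm". It does not say who judges relatedness or by what rule, and it gives no time window, rate by arm, risk difference or confidence interval. The Main Analysis paragraph just above it does say that participants are grouped by allocated arm.

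The SAP's Descriptive Analysis section has a general rule: "we will explore and describe the outcome variables overall and grouped by study arm". The approach is the one used for cohort descriptors, where "Groups will not be formally compared used statistical tests; differences and confidence intervals of differences may be reported". Safety is neither named nor excluded.

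Protocol section 6 says "Complications related to clinical care are being captured routinely as outcomes and will be reported to the IRB as appropriate" and "The PI will also record adverse events and serious adverse events". It states no analysis by arm. Protocol section 5 says that patients and providers are unblinded while outcomes are analyzed by a blind assessor, and that usual-care patients choose their own position, which is expected to be mostly supine or semi-recumbent.

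**The concern.** Falls, vomiting and accidental line displacement happen to hospital patients in any position. A fair comparison of advice to prone with usual care needs the same events counted by the same rule in both arms. A filter on relatedness to proning breaks this. An event in a patient who was not prone is unlikely to pass, and such patients should be concentrated in usual care. Whether an event enters the numerator then depends on the arm, and randomization does not protect against that.

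The comparison matters here because the protocol states that participation adds no treatment-related risk (section 6), seeks a waiver of consent on minimal-risk grounds (Regulatory Considerations), and generally gives patients no option to withdraw themselves (section 7). An unfiltered comparison by arm would test the minimal-risk premise.

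**Working it through.** **1. The passages side by side**

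- Endpoint: complications of positioning, in any participant.
- Safety analysis: all participants in the denominator, but only proning-related events in the numerator.
- Descriptive rule: outcome variables by arm, with differences and intervals optional.

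Applying the third rule to the second gives a table by arm of filtered counts. It settles how the counts are tabulated and leaves the filter in place. Returning to the endpoint's wording would widen the filter but would still require a relatedness judgement.

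**2. Number of patients**

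The documents state no safety rate or safety sample size, so there is no safety figure to reproduce. The size of the safety sample follows from the primary endpoint: 250 per arm × 2 = 500; 500 × 1.10 = 550; 550 / 2 = 275 per arm, taking allocation by record number as roughly 1:1.

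As a check on the 500, the Whitehead formula is N = 12(z_α + z_β)² / [ln(OR)² (1 − Σp̄³)]. Inputs are OR 1.6, 80% power, the pre-trial day-5 distribution in Protocol section 8, and an assumed two-sided 0.05 (no alpha is stated). This gives 12 × (1.960 + 0.842)² / [0.2209 × 0.8804] ≈ 484, and power of 81.2% at N = 500. That is close to the stated 80%. It does not bear on the safety wording.

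**3. Effect of the filter (all rates assumed)**

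Let n be patients per arm, r the true event rate and s the share of events judged proning-related. Then counted events = n × r × s, and the counted ratio = (r_P × s_P) / (r_U × s_U), with P for prone and U for usual care.

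Take n = 275, r = 5% in both arms and s_P = 1. The prone arm counts 275 × 0.05 × 1 = 13.75.

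| Share counted in usual care, s_U | Usual-care events counted | Prone-arm events counted |
|---|---|---|
| 1 | 13.75 | 13.75 |
| 0.5 | 6.875 | 13.75 |
| 0 (extreme) | 0 | 13.75 |

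At s_U = 0.5 the apparent rates are 5.0% and 2.5%, a ratio of 2 when the true ratio is 1. The apparent difference is 2.5 points, with SE = √(0.05 × 0.95/275 + 0.025 × 0.975/275) = 0.0162 and 95% CI −0.7 to +5.7 points. The harm lies in a misleading estimate; it need not reach significance.

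**4. What an unfiltered table by arm could show (assumed rates, 275 per arm, two-sided 0.05)**

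Power = Φ{[d − 1.96√(2p̄(1 − p̄)/n)] / √[(p_U(1 − p_U) + p_P(1 − p_P))/n]}. For 1% versus 2%: (0.0100 − 1.96 × 0.01037) / 0.01036 ≈ −1.00, so power is 16%. The CI is d ± 1.96√[(p_U(1 − p_U) + p_P(1 − p_P))/n].

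| Usual care vs prone | Power | 95% CI for the difference, if observed (points) |
|---|---|---|
| 1% vs 2% | 16% | −1.0 to +3.0 |
| 2% vs 4% | 28% | −0.8 to +4.8 |
| 5% vs 10% | 60% | +0.6 to +9.4 |
| 10% vs 20% | 91% | +4.1 to +15.9 |

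Such a table is informative for common events and imprecise for rare ones.

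**The case against.** A reader might infer that the SAP pools the arms, so that the trial cannot show any difference in complications. The documents do not support that. The phrase about study arm sits under Datasets, which defines who is included, and it follows the statement that all participants are included. The natural reading is that proning events count in usual-care patients too. The SAP uses a similar phrase in that sense in Descriptive Analysis, for nurses' estimates of prone hours. Arm is known for every participant, and the general descriptive rule can be read to cover safety.

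A reader might also infer that usual care would show near zero by definition, or that unblinded staff apply the filter. Neither is established. Usual-care patients may prone by choice, and both documents anticipate crossover, so some of their events would qualify. No passage says who judges relatedness; the protocol has a blind assessor analyze outcomes but does not give that assessor this judgement.

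It is also fair to say that Protocol section 6 captures complications more widely and that the SAP's safety analysis is openly exploratory. Background events need not be missing from the trial's records.

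All of this stands against the stronger readings. None of it removes the filter: events captured in both arms but counted only if proning-related still leave out background events in patients who were not prone.

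**Conclusion.** The concern holds in limited form. The safety analysis is narrower than its own endpoint, filters events by relatedness to proning without a rule, and does not itself commit to a comparison by assigned arm. Following it could give a distorted comparison even if the general descriptive rule is applied. The plan therefore does not secure an unbiased estimate of the effect of advice to prone on falls, vomiting and line displacement; whether the trial's data could support one is a separate question.

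The likely direction is to make proning look worse, because a larger share of usual-care events would be left out. The size is unknown. The doubling shown above rests on an assumed 5% rate in both arms and an assumed half of usual-care events failing the filter; with equal shares in the two arms the ratio would not be distorted. This is a cheap improvement to the plan and does not touch the primary analysis.

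**What to change.** In the SAP:

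- Reconcile the wording of the safety endpoint (positioning) with that of the safety analysis (proning).
- Count every accidental line displacement, vomiting episode and fall in every participant, whatever the position at the time and whatever the attribution.
- Use the same fixed window from enrollment in both arms, and state how patients discharged within it are handled.
- Report by assigned arm: patients with at least one event, the risk difference and its 95% CI.
- Keep the description of proning-related events as a supplement and state who judges relatedness.

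The cost is SAP wording, one table and modest extra abstraction from the medical record for events not attributed to position. The table would be imprecise for rare events, as the power figures above show, so it should be presented as estimates with intervals, and a lack of significance should not be read as evidence of safety.

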This study will be performed as a pragmatic controlled clinical trial. Patients fitting inclusion criteria who are admitted to the Vanderbilt University Adult Hospital will be enrolled in this study. Individual patient-level quasi-randomization will be employed. Odd-numbered MRNs will be assigned to the prone positioning and even-numbered MRNs will be assigned to the usual care arm. COVID-19 admissions will be reviewed during the daily COVID huddle, and appropriate study team personnel will facilitate protocol execution, working with the local providers/units.

5. Study Procedures

The study procedures in place involve treatment assignment, as well as electronic data capture. Day zero will be defined as the day of enrollment and treatment assignment. Data will originate from the electronic medical record for all patients, as well as from non-invasive patient wearable positioning sensors for a random subset to ensure protocol fidelity. Patients will be assigned to either one of the two comparator arms. Patients and providers will necessarily be unblinded, but outcomes will be analyzed by a blind assessor. Study arm assignment and the corresponding protocol will be discussed at the beginning of each day during the daily COVID-19 huddle. Workflow will include an initial run in period as we expect implementation uptake to take time. Patients enrolled during this ramp-up and optimization period will be allocated to

Study Protocol: Version 7.0 - October 29, 2020

Full Study Title: Pragmatic Trial Exploring Impact of Patient Positioning in the Management of Patients Infected with COVID19: Supine vs. Prone

Primary Investigator: [name], MSc

either the prone or usual care group as appropriate, but their data will not be included in the final analysis.

Comparator Arm A: COVID-positive patients who require supplemental oxygen, but are not yet mechanically ventilated, will be encouraged to lay in a completely prone position for as much time as is tolerable during hospitalization. Guidelines to ensure standardization include the following:

- Instructions to care-giving teams on how to frame the prone positioning ask to patients
- Request that clinical team provide reminders to the patient to prone if they are able (as feasible given workloads)
 - Suggest putting a pillow under pelvis/abdomen and under the lower legs to alleviate lower back strain
 - Suggest listening to podcast, music, or audiobook

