Subgroup analyses and differential treatment effects

To determine whether effects of treatment depend on any of the baseline characteristics, we will test the interaction between the characteristic and treatment effect in the PO model. Only if it is significant will we conduct a separate subgroup analysis. In this case, we will be liberal when considering whether a potential effect modifier has an interaction with the treatment, using a p-value of <0.2 . For continuous variables, of which age is the primary variable of interest, we will not create artificial groups but instead we will present the partial effect plots demonstrating how the treatment effect changes over age. If warranted, a subgroup analysis may be conducted using the same model as for the primary outcome, but with the subgroup-defining variable removed from the model. We will not adjust subgroup analyses for multiplicity, but all data reports will clearly indicate the potential for false positive findings. We will focus these subgroup analyses on estimates of potential group specific effects rather than significance testing. Any findings will be subject to further confirmatory studies. Subgroup analyses will be performed using the intention to treat sample.

Summary

The analyses described here are those necessary to answer the trial's primary question of whether advising patients to prone is more effective than usual care in improving clinical status five days after being hospitalized for Covid-19 with requirements for supplemental oxygen. Beyond our analysis exploring the effect of treatment on primary, secondary, and exploratory endpoints, we expect there to be multiple additional exploratory analyses conducted, in particular as they relate to the supplementary study and understanding the association between objective measures of proning and moment-to-moment oxygen levels. It is not possible to predetermine the nature of such analyses. However, we are committed to preserving rigor and reproducibility and will pre-specify each subsequent analysis in the context of the specific question to be answered, cognizant of bias and missingness in the data.

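### The analysed population is not fixed: the observed result decides whether single-site data are reported, and the SAP omits the protocol's exclusion of run-in patients

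*SAP*

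**What the plan says.** **Site rule.** Under Datasets, Main Analysis, the SAP defines an intention-to-treat set: "All participants who met inclusion criteria and were randomized will be included". Under Sensitivity analysis it explains that the trial began as a single-center study and that "One additional site was opened, which contributed less than 10% of participants to the dataset". It continues: "We will repeat our main analyses excluded this additional site". The next sentence is the reporting rule: "If there are considerable differences, then we will report single site data". The SAP does not name the quantity to be compared, define what counts as considerable, or say whether single-site results replace the all-site results or accompany them. The subgroup section says "Subgroup analyses will be performed using the intention to treat sample".

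**Run-in.** Protocol section 5 (Study Procedures) says "Workflow will include an initial run in period as we expect implementation uptake to take time". Patients enrolled in that period are allocated to "either the prone or usual care group as appropriate, but their data will not be included in the final analysis". The fidelity-monitoring paragraph of the same section mentions a run-in again: "An initial run-in period will inform appropriate sensor assignments for the remainder of the study duration". The SAP mentions no run-in or ramp-up. Neither document gives the run-in's end date or number of patients, or says whether these patients count towards the planned 550. The reasons given for the 10% increase from 500 to 550 (protocol section 8; SAP, Population and Design Considerations) are missing data, crossover and the position sensors. Run-in exclusions are not among them.

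**The concern.** A sensitivity analysis should test the headline result. It should not decide which dataset supplies the headline. Here the trigger is the observed difference between two estimates, one of which contains more than 90% of the other's patients. If both sites share the same true effect, that difference is chance. The SAP's reasons for examining the site (originally single-center, under 10% of participants) do not depend on results, so the reporting rule can be fixed in advance. If the rule fired and single-site data became the headline, the headline and the subgroup results would come from different patients.

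The run-in gap concerns the same question of who is analysed. An analyst working from the SAP alone would include the run-in patients. One working from both documents would exclude them, but would find no date at which the exclusion stops. A cut-off with no date could be chosen after outcomes are known.

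**Working it through.** **Inputs.** OR 1.6, 80% power, 500 patients in total, raised to 550 (protocol section 8; SAP, Population and Design Considerations). Added site under 10% of participants (SAP). The documents state no alpha, so two-sided 0.05 is assumed, in line with the 95% confidence intervals in the SAP. Also assumed: a site share s of 5% or 10%, a trigger of 1, 1.5 or 2 SD of the difference, and 50 or 100 run-in patients.

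**The plan's own figure.** The post-interim outcome distribution is not given, so I used the protocol's planning distribution (40/10/30/14/5/1%, best to worst). The Whitehead formula is N = 12(1.960 + 0.842)² / [(ln 1.6)² (1 − Σp̄³)]. With Σp̄³ = 0.12 it gives N = 484, and 81.2% power at 500. This is close enough to the stated 500 and 80% to use the stated pair for calibration.

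**Precision**
- SE of the log OR at 500: ln(1.6)/2.8016 = 0.4700/2.8016 = 0.1678.
- At 550: 0.1678 × √(500/550) = 0.160.

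**Site rule**
- SD of the difference between single-site and all-site log OR = 0.160 × √(1/(1 − s) − 1). This is 0.037 at s = 5% and 0.053 at s = 10%. On the OR scale, 1 SD is a shift of 4–5% and 2 SD a shift of 8–11%.
- SE of the added site's own log OR = 0.160/√s: 0.72 (about 28 patients) or 0.51 (55 patients).
- Simulation under the null, 4 million draws, with the single-site result reported in place of the all-site result when the trigger is crossed:

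| Trigger | Fires by chance | Overall type I error, s = 5% / 10% | Type I error when it fires, s = 5% / 10% |
|---|---|---|---|
| 1 SD | 32% | 5.3% / 5.5% | 5.8% / 6.7% |
| 1.5 SD | 13% | 5.2% / 5.4% | 6.7% / 8.3% |
| 2 SD | 4.6% | 5.1% / 5.3% | 7.8% / 10.5% |

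- In the trials where the rule fires, the all-site result still has a type I error of about 5.0%. Free choice between the two results would give 6.0–6.5%.
- Power at OR 1.6 = Φ(2.8016 × √(N/500) − 1.96): 83.6% for all 550, 81.7% for the single site at s = 5%, 79.6% at s = 10%.

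**Run-in.** Let r run-in patients, counted within the 550, receive a fraction u of the log OR.
- Excluded: Φ(2.8016 × √((550 − r)/500) − 1.96).
- Included: Φ(2.8016 × √(550/500) × [1 − (r/550)(1 − u)] − 1.96).

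| r | Excluded | Included, u = 0 | u = 0.5 | u = 1 | Break-even u |
|---|---|---|---|---|---|
| 50 | 80.0% | 76.2% | 80.1% | 83.6% | 0.49 |
| 100 | 75.7% | 67.2% | 76.2% | 83.6% | 0.47 |

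If the run-in patients are instead additional to the 550, excluding them leaves 550 analysed and power at 83.6%.

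**The case against.** **Replacement is one reading.** The sentence does not say that single-site data are reported instead of all-site data. It sits under a sensitivity heading, and the main-analysis paragraph is unconditional. If the single-site result merely accompanies the all-site result, type I error is not inflated. That is correct, and the error rates above apply only to replacement. Even on the milder reading, whether the single-site result is shown depends on what it finds, and the same sentence cures both.

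**The triggers are small.** A 4–5% shift in the OR is hardly considerable. With a 10% shift as the trigger, chance firing falls to 0.9% (5% share) or 7.4% (10% share). With a 15% shift it is about 0.01% or 0.9%, and overall type I error is close to 5.0–5.1%. This stands as a limit on size. But the SAP sets no threshold, so none of these can be assumed.

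**Sites may really differ.** Protocol section 8 notes that institutions vary in how they use supplemental oxygen, which is what the endpoint measures. That is a good reason to show the single-site result every time. It is no reason to make reporting depend on the result, and the added site's SE of 0.51–0.72 means its data could hardly tell a real difference from noise.

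**The run-in may be small, or the exclusion dropped on purpose.** The counts used here are assumed, and the SAP (January 2021) is later than protocol version 7.0 (October 2020). Both points are fair, but the SAP does not say that the exclusion was withdrawn, so the two current documents conflict.

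**Conclusion.** Both parts hold. The SAP makes the reporting of single-site data depend on an undefined observed difference, and its analysis set contradicts the protocol on run-in patients. Nothing elsewhere in either document resolves these points.

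The site rule matters more in principle than in numbers. Overall type I error stays at about 5.1–5.5% under the assumed triggers and could not exceed about 6.5% even with free choice between the two results. These figures assume replacement, a common true effect at both sites and a site share of 5–10%. The run-in effect has no knowable size or direction from the documents. Including those patients lowers power if they received less than about half of the full log-OR effect and raises it if they received more. The firm finding there is that the primary analysis population is undefined. The SAP should be corrected on both points.

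**What to change.** 1. Delete the conditional sentence on single-site data. State that the all-site intention-to-treat analysis is primary whatever the site comparison shows, and that the analysis without the added site is always reported beside it and never substituted for it. Adding site as a covariate is preferable but not essential.
2. Reconcile protocol section 5 with the SAP's Main Analysis dataset. Carry the run-in exclusion into the SAP for both arms, with a calendar cut-off taken from implementation records without reference to outcomes. State how many patients it removes and whether they count towards the 550. Report the analysis that includes them as a sensitivity analysis. If the exclusion was deliberately dropped, the SAP must say so and give the reason.

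**Cost.** The change is SAP wording, plus one degree of freedom if site is added. The sponsor gives up the option of dropping the added site. If run-in uptake was already full and these patients sit within the 550, excluding them costs 83.6 − 80.0 = 3.6 points of power for 50 patients, or 83.6 − 75.7 = 7.9 points for 100. If they are additional to the 550, excluding them leaves the planned 550 intact.
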